1.0 Objectives

1.1 Describe the purpose, specific aims, and/or objectives.

The goal of this research is to determine if the Tangible Boost system adequately replenishes the HydraPEG coating on the surface of a rigid contact lens. HydraPEG is a soft and rigid contact lens coating, primarily composed of polyethylene glycol, which is covalently bound to the surface of a contact lens. The HydraPEG coating is intended to improve wettability and comfort with rigid lenses, and is currently FDA approved. HydraPEG can be applied to soft or rigid contact lenses, but the coating naturally diminishes from the surface of the lens over time (due to cleaning, and blinking over the surface of the contact lens). Tangible Science, the company that produces HydraPEG, has recently come out with a new product called Tangible Boost, intended to be used every 30 days and replenish the coating on the surface of the lens.

Tangible Boost (also known as HydraPEG Replenish in some of the FDA documents) is a solution composed on the same components of the HydraPEG coating). Essentially, Tangible Boost solution is the HydraPEG coating, it is just in solution that can be used at home by the subjects after the initial HydraPEG is applied at the lens manufacturing lab. The Tangible Boost kit consists of two unit dose HydraPEG solutions (components A and B), as well as a barrel case, and the lens wearers are instructed to empty the two vials into the case and soak their lenses for 30 minutes every 30 days to replenish the coating. This product configuration has been optimized to facilitate ease of use for the patient.

This is a study to evaluate the efficacy of Tangible boost to replenish the HydraPEG coating on rigid gas permeable (scleral and corneal) contact lenses.

1.2 State the hypotheses to be tested.

We hypothesize that the Tangible Boost replenishing system will re-build the HydraPEG coating that naturally diminished from the contact lens surface over time, and improve the comfort and visual performance of HydraPEG coated rigid gas permeable lenses. We anticipate that this be shown by improved patient symptoms and lens wettability after treatment with Tangible Boost.

2.0 Background

2.1 Describe the relevant prior experience and gaps in current knowledge.

Page 3 of 22 Revised: July 24, 2017

Gas permeable rigid contact lenses are commonly used as refractive treatment, for normal individuals, but also specifically for individuals with irregular ocular surfaces that require the rigid lens material to mask irregularities on the front refracting surface of their eye (the cornea). However, these lenses rely on surface treatments and coatings in order to improve their interactions with the front surface of the eye and the tear film, which are very sensitive tissues that can respond negatively to the rigid materials (for example: discomfort, dryness). Several studies have found that reducing the friction between the lens and the surface of the eye (as well as the eyelid) will improve the comfort of the lens while a patient is wearing them. The primary principle behind HydraPEG coating and Tangible Boost replenishing system is that they reduce friction between the lens and the eye surface and eyelids.

Contact lens manufacturers and distributors are continuously developing new products and technology to make the surface of a contact lens more compatible with the ocular surface. HydraPEG is a newly FDA approved coating that is available in the US and Europe, and the Tangible Boost treatment being evaluated here is an important component of maintaining this treatment of the lens surface.

2.2 Describe any relevant preliminary data. Reference previously approved IRB protocols (by number), if applicable.

Hydra-PEG (Ocular Dynamics, Menlo Park, CA) is a contact lens coating designed to improve the lens/ocular surface interface by mimicking the natural tear film's water content and wettability. A previous study done at UH showed that the coating improved comfort and vision when applied to scleral contact lenses. (ID# 16071-01). The Hydra-PEG coating is FDA approved for use as a contact lens coating.

2.3 Provide the scientific or scholarly background for, rationale for, and significance of the research based on the existing literature and how will it add to existing knowledge.

Knowledge gained by this work will increase our understanding of the surface characteristics of rigid lenses and the interaction of the lens surface with the ocular surface.

3.0 Inclusion and Exclusion Criteria

3.1 Describe the specific criteria that define who will be included or excluded in your final study sample. Make sure to include age.

Page 4 of 22 Revised: July 24, 2017

The participant will be eligible to participate if the following criteria apply: 1. Written Informed Consent has been obtained prior to any study-related procedures taking place; 2. Written documentation has been obtained in accordance with the relevant county and local privacy requirements, where applicable (i.e., Written Authorization for Use and Release of Health and Research Study Information to obtain contact lens prescription and wearing information from their medical record should the subject be a patient at the UH College of Optometry); 3. Male or female,18 years of age and older prior to the initial visit; 4. Is an established scleral or corneal rigid contact lens wearer; 5. In the opinion of the investigator, the subject has the ability to follow study instructions; 6. In the opinion of the investigator, the subject has the ability to complete all study procedures and visits.

The participant would not be eligible to participate if at least one of the following criteria is met: 1. Has never worn either scleral or corneal contact lenses before; 2. Does not possess a usable pair of spectacles; 3. Has any ocular disease or abnormality that would affect the wearing of contact lenses; 4. Is aphakic (i.e., missing their natural lens inside the eye); 5. Is currently participating in any other type of eye-related clinical or research study; 6. Is pregnant or nursing as reported by the subject. 7. Has a condition or is in a situation which, in the investigator's opinion, may put the subject at significant risk, may confound study outcomes, or may significantly interfere with the subject's participation in the study. 8. Has a known and self-reported allergy to the following substances: Dextran, polyethylene glycol, hydroxypropyl methylcellulose, or polyvinyl alcohol, which are components of the Tangible Boost and HydraPEG systems. 9. Has had previous ocular surgery within the past 12 weeks.

3.2 Describe how potential subjects will be screened for eligibility based on these criteria.

Subjects will be screened as either corneal or scleral CL wearers prior to coming in for visit 1 of the study, either in person, over email, or over the phone when they show interest in the study. The screening for ability to wear a rigid lens in the study will occur at visit 1 by the investigator, when the subjects are diagnostically fit with a scleral or corneal lens (whichever modality they habitually wear).

3.3 Indicate specifically whether you will include or exclude each of the following special populations: (You may not include members of the populations listed below as subjects in your research unless you indicate this in your inclusion criteria.)

The following special populations will be excluded from this study:

Page 5 of 22 Revised: July 24, 2017

- Adults unable to consent
- Individuals who are not yet adults (infants, children, teenagers) -
- Pregnant women
- Prisoners

4.0 Vulnerable Populations

4.1 If the research involves individuals who are vulnerable to coercion or undue influence, describe additional safeguards included to protect their rights and welfare.

Students may be recruited for participation in this study (if they wear rigid corneal or scleral lenses habitually), and the investigators on this study are instructors in the clinic at UHCO. These investigators will not be the individuals recruiting or obtaining consent from students in their own clinical student group at the time of the study. There will be no influence on grading of any student based on their participation or non-participation in this study.

5.0 Number of Subjects

LOCAL:

5.1 Indicate the total number of subjects to be accrued locally.

A maximum of 40 subjects will be enrolled in this pilot study.

5.2 If applicable, distinguish between the number of subjects who are expected to be enrolled and screened, and the number of subjects needed to complete the research procedures (i.e., numbers of subjects excluding screen failures.)

We expect about a 20% screen fail/drop out rate, so will expect to recruit approximately 35-40 subjects, and the first 30 to be eligible and complete the study will be used for data analysis.

5.3 If not provided in the "study-wide" section, provide justification for the number of subjects. A power analysis is required for research that is more than minimal risk.

Page 6 of 22 Revised: July 24, 2017

This is a low risk study; there are limited data collected in other studies on rigid lens wear with the HydraPEG coating, so the data collected in this preliminary study will be used for future power calculations for larger studies. We chose 30 subjects to allow for an increased likelihood of reaching significance values with a moderate sample size. Further studies with larger sample sizes will likely be indicated if variability is high among the outcomes.

6.0 Recruitment Methods

LOCAL:

6.1 Describe when, where, and how potential subjects will be recruited.

Recruitment will begin once IRB approval has been received, and will occur through The Ocular Surface Institute at UHCO. Subjects will be recruited through the methods described in 6.3, and if a patient is interested in participating in the study, they will be directed to the principal investigator or the study coordinator who will go over the study and ask the screening questions on the eligibility screening document (see appendix). If they are eligible based on the screening criteria, they will be invited for Visit 1 of the study. If the person calls to learn about the study the investigator or coordinator will use the outline to determine initial eligibility.

6.2 Describe the source of subjects.

Our study will involve established rigid contact lens wearers (corneal or scleral). The subject pool will consist of patients who are actively coming through the CL clinic, or individuals who are affiliated with UHCO and/or the UH community (ie. Faculty, students). All established corneal and scleral lens wearers in the community will be given the opportunity to participate in this study. We anticipate that most of our subjects will be from the patient population in the specialty contact lens service at the University Eye Institute at UHCO, which has a high population of rigid lens wearing patients actively coming through the clinic. We will not be doing a chart review and calling patients who are not coming into the clinic. Patients that do not come into the clinic but hear about it by word-of-mouth or through a UHCO affiliate are welcomed to participate.

6.3 Describe the methods that will be used to identify potential subjects.

Page 7 of 22 Revised: July 24, 2017

A recruitment ad will be printed (see appendix) and will be placed on bulletin boards around the UHCO campus (there are specific boards designated for study announcements on the campus), and at the check-in counter at the cornea and contact lens service at the University Eye Institute. In addition, the study coordinator will email a copy of the recruitment ad to the faculty and staff at UHCO (not the entire university). Clinicians working at the UEI may speak to patients and/or give them a copy of the recruitment advertisement to review.

6.4 Describe materials that will be used to recruit subjects.

See appendix for recruitment advertisements to be posted and emailed, and a phone and in-person eligibility screening outline.

7.0 Multi-Site Research Communication – N/A

8.0 Study Timelines

8.1 Describe:

The total duration of the subjects' participation in the study will be approximately 5 months. It is anticipated that to enroll all study subjects it will take approximately 4-6 months. The estimated date for completion of this study is 11-12 months after the start of recruitment.

- Visit 1: The total time commitment required is approximately 100 minutes once informed consent has been commenced until the last test is completed.
- Visit 2: The total time commitment required is approximately 45 minutes until the last test is completed.
- Visit 3: The total time commitment required is approximately 85 minutes until the last test is completed.
- Visit 4: The total time commitment required is approximately 25 minutes until the last test is completed.
- Visit 5: The total time commitment required is approximately 25 minutes until the last test is completed.

9.0 Study Endpoints

- 9.1 The primary endpoints in this study are as follows:
 - visual acuity
 - contact lens comfort questionnaire
 - keratograph surface evaluation (tear break up score)
 - ocular surface staining

Page 8 of 22 Revised: July 24, 2017

- 9.2 The secondary endpoints in this study are as follow:
 - contact lens fitting characteristics (apical clearance, limbal clearance, scleral landing evaluation)

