The solution will be dispensed and the subjects trained on its use, and the subjects will be asked to store their lenses in the given solution for 30 minutes that evening, and then transfer their lenses to Unique pH multipurpose rigid lens solution for overnight storage. For the initial training with the Boost or placebo system, the users will undergo an approximately 60-minute user training in which there will be visual and audio recording and still photographs taken in order for a human factors company (Userwise) to analyze the usability of the product. The investigator at the study visit will act as the monitor for the training session. This recorded training step was specifically designed to allow for proper evaluation of the usability of the product, which they will report to the FDA to ensure usability. At the initial visit, the subject will have indicated on the informed consent form whether they agree to participate in the recorded portion of the training. If they do not participate in the recording, they can still be trained and participate in the study.

The subjects will report to the Ocular Surface Institute the next day for Visit 4, at which time the comfort and visit tests will occur again, and an additional survey to evaluate the boost treatment will be given. After visit 4, the subjects will continue to wear the study lenses daily for an additional 60 days, treating their lenses again in the Boost or placebo solution at the midpoint between visit 4 and 5 (30 days after the first treatment with Boost), otherwise cleaning nightly with ClearCare, and will then report to the clinic again 30 days after the midway treatment (approximately 90 days after the initial HydraPEG dispense). The same visit testing will be done at this final and 5th visit, and a final short survey will be done, and then the lenses will be collected from the subjects and sent back to Tangible Science, Inc. for their internal testing of the lenses (no involvement of the UH research team). At this time the study will conclude.

The following table outlines each of the study visits and tells what procedures will be done at each visit:

Procedure	Length of Time Required for	Frequency of Repetition
VISIT 1: Initial Evaluation		
Informed consent & HIPAA	35 minutes	Once
General History and medications	5 minutes	Once per visit
Visual Acuity	5 minutes	Once per visit

Page 10 of 22 Revised: July 24, 2017

Questionnaires (CLDEQ8 + VAS)	10 minutes	Once per visit

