Statistical Analysis: Each individual will act as their own control to measure differences in pre and post contact lens measurements (paired non-parametric statistics), and this baseline data will be compared to normative data available for a soft contact lens wearing population. Descriptive statistics will also be employed to evaluate the overall response of the eye to a rigid lens with and without HydraPEG and with and without Tangible Boost.

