24.0 FERPA - N/A

25.0 Data Management

25.1 Describe the data analysis plan, including any statistical procedures.

Data will be stored in a study paper file. Paper files will be kept in a filing cabinet within The Ocular Surface Institute (Health and Biomedical Sciences Building). Electronic data will be stored on a password-protected computer in a locked office in rooms 232, 236 or 250 within The Ocular Surface Institute of the Health Biological Sciences Building (HBSB). All study data will remain on UH property within The Ocular Surface Institute for a minimum of 3 years following study completion. The principal investigator will be

Page 20 of 22 Revised: July 24, 2017

responsible for maintaining study data security and subject confidentiality, and the PI and the study coordinator will be responsible for receipt and transmission of the data. The investigative team, study sponsor and inspectors from regulatory agencies such as the US Food and Drug Administration will have access to the data if requested for study monitoring or an audit.

All collected data will be documented on study documents and analyzed for differences between baseline and test data. Hypothesis testing will be performed using statistical analyses including parametric or nonparametric comparisons (i.e., t-tests, signed-rank tests), analysis of variance, general linear models, correlation, or regression techniques.

The recorded audio and video data will be sent to UserWise for analysis of the usability of the product.

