Over refraction (spherical only) OD OS			
OD OS			os
OS Slit Lamp Evaluation of Study Lense	es Movemei Centratio Apical Cleara	on	os

Subject:		
ate:	/	
System		

	THE O	CULA	AR SURFACE INSTITUTE	Date://
	1	Eva	luation of Tangible Boost Replenishing	g System
			Scleral Landing Zone	
11.	Perforr	n Kera	atograph NIBUT	
		OD:	NIKf-BUT "until blink" (first break up) NIKavg-BUT "until blink" (average break up) Level:	
			NIKf-BUT "25 seconds" (first break up) NIKavg-BUT "25 seconds" (average break up) Level:	
		OS:	NIKf-BUT "until blink" (first break up) NIKavg-BUT "until blink" (average break up) Level:	
			NIKf-BUT "25 seconds" (first break up) NIKavg-BUT "25 seconds" (average break up) Level:	
12.	Are len	ises st	ill adequate to be worn? \square_1 Yes \square_2 No	
If no,	, please in	ndicat	ed parameter changes indicated below:	
13.			st Training and Video recording	
	а.	Video	o file name (camera)	
			o file name (go-pro)	
	c.	Video	is uploaded to share drive? \square_1 Yes \square_2 No	

UNIVERSITY of HOUSTON

THE OCULAR SURFACE INSTITUTE

[figure not shown]
Date:	/	/
		,

Evaluation of Tangible Boost Replenishing System

[figure not shown]
- d. Videos uploaded to Dropbox?
- \square_1 Yes □₂ No
- 14. **Tangible Boost or Placebo Kit Training**
 - a. Boost/Placebo dispensed? \square_1 Yes \square_2 No
 - b. Boost Log form filled out? \square_1 Yes \square_2 No
 - c. Boost Lot #:
- **15.** Removal of lenses and Slit lamp exam (after lens removal)

Corneal Fluorescein Staining (0-4 grading) 16.

TOTAL Score: OD _____ OS ____

- Dispensed Unique pH? \square_1 Yes \square_2 No **17.**
- 18. Dispensed DMV? \square_1 Yes \square_2 No
- **Dispensed PuriLens?** \square_1 Yes \square_2 No 19.

Sub	ject:		
Date: _	/	/	

20.	Gift card given?	□₁ Ye	S	□ ₂ No	1
21.	Follow up appt in 1 day	/?	□ ₁ Ye	!S	\square_2 No
22.	Follow up appt date:				

THE	OCIII	ΔR	SLIRFA	CF	INSTITU	ITE

Subject:		
Date:	_/_	/

VISIT 4

1.	Time of Day (military time) ::					
2.	Hours of lens wear today:					
3.	Current Cleaning solution:					
4.	Currently wearing study lenses? \Box_1 Yes	\square_2 No	0			
5.	CLDEQ-8a. CLDEQ-8 completed and verified:	□₁ Yes	□ ₂ No	CLDEQ-8 score:		
6.	VAS scale a. VAS scale completed and verified:	□ ₁ Yes	□ ₂ No	VAS score:		
	b. Extended VAS scale completed:	\square_1 Yes \square_1 Yes	\square_2 No \square_2 No \square_2 No \square_2 No \square_2 No	removal:vision:		
7.	Medications a. Any changes in medications? b. If yes, please specify:		es \square_2 No			

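### Four unranked primary endpoints, two post-treatment visits and an undefined break-up score are open to testing with no stated alpha or multiplicity control, so the false-positive rate is substantially inflated

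*Combined protocol and SAP*

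**What the plan says.** Section 9.1 begins "The primary endpoints in this study are as follows" and lists visual acuity, a contact lens comfort questionnaire, "keratograph surface evaluation (tear break up score") and ocular surface staining. It does not rank them or say whether one, some or all must succeed.

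Section 10.1 places two visits after treatment. For the first: "The subjects will report to the Ocular Surface Institute the next day for Visit 4". Visit 5 comes 30 days after a second treatment. Neither is named as the primary time point.

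The visit worksheets do not define a single break-up score. For each eye they record first and average break-up time in two modes (until blink, and 25 seconds), plus a level for each mode; one such entry is "NIKavg-BUT '25 seconds' (average break up"). The comfort measures are CLDEQ-8, a VAS and visit-specific secondary VAS scales. Both eyes are measured, and no rule combines or selects them.

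On analysis, section 10.2 says "Each individual will act as their own control to measure differences in pre and post contact lens measurements (paired non-parametric statistics"), and section 25.1 says "Hypothesis testing will be performed using statistical analyses including parametric or nonparametric comparisons (i.e., t-tests, signed-rank tests"), followed by analysis of variance, linear models, correlation or regression. No alpha, testing order or multiplicity adjustment appears anywhere. Section 5.3 gives this reason for the sample size: "We chose 30 subjects to allow for an increased likelihood of reaching significance values with a moderate sample size".

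**The concern.** If several measures, visits and readings can each be tested at the full level and any one can be reported as a primary result, the error rate of the whole set exceeds that of a single test. Nobody reading a significant result could tell whether it was the intended test or the most favourable of many.

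There is a second consequence. Section 5.3 says these data will feed power calculations for later studies. An effect carried forward because it was the best of several would tend to be too large, and the later study would then be too small.

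**Working it through.** **Inputs from the documents.** Four primary endpoints (9.1); two post-treatment visits (10.1); four break-up times and two levels per eye (worksheets), so 6 values per eye and 12 per visit; 30 analysed subjects (5.2).

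**Assumptions, not in the documents.** Two-sided 5% per test, hence 2.5% in Boost's favour; 1:1 allocation, hence 15 per arm; equal pairwise correlations of 0.3 to 0.7 between tests; each test a valid comparison of Boost with placebo.

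**The plan's own figure.** No error rate or power is stated. The only design figure that can be reproduced is recruitment: 30 / (1 − 0.20) = 37.5, rounded up to 38, which lies within the stated 35–40. It has no bearing on multiplicity.

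**Independent tests.** The chance of at least one false positive among m tests is 1 − (1 − α)^m.

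- m = 4 (four endpoints, one visit): 1 − 0.95^4 = 0.185. In Boost's favour only: 1 − 0.975^4 = 0.096.
- m = 8 (four endpoints, two visits): 1 − 0.95^8 = 0.337. In Boost's favour only: 1 − 0.975^8 = 0.183.

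**Correlated tests.** The same probabilities for equicorrelated normal test statistics, critical value 1.96:

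| Correlation | 4 tests, either direction | 4 tests, favouring Boost | 8 tests, either direction | 8 tests, favouring Boost |
|---|---|---|---|---|
| 0 | 18.5% | 9.6% | 33.7% | 18.3% |
| 0.3 | 17.4% | 8.7% | 30.0% | 15.2% |
| 0.5 | 15.6% | 7.8% | 25.0% | 12.5% |
| 0.7 | 13.0% | 6.5% | 19.1% | 9.5% |

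Against the nominal 2.5%, the Boost-favouring rates run from 6.5 / 2.5 = 2.6 times to 18.3 / 2.5 = 7.3 times.

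**Break-up score alone.** Taking the best of the four times, in one eye at one visit, at assumed correlations of 0.9 to 0.6, gives 9.4–14.4% in either direction and 4.7–7.2% in Boost's favour. The counts of 4 and 8 above treat the break-up score as one test. Counting the four times separately gives 4 − 1 + 4 = 7 measures, or 14 tests over two visits: 1 − 0.95^14 = 51.2% if independent (29.8% in Boost's favour). Under structured correlations (0.2–0.5 between endpoints, 0.7–0.9 between break-up readings, 0.5–0.8 between visits, all assumed) simulation gave 28–41% (14–21% in Boost's favour).

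**Cost of adjusting.** For a two-sample t-test with 15 per arm and 80% power, the detectable difference is 1.06 SD at 5% and 1.29 SD at 0.05 / 4 = 1.25%, the first Holm step with four endpoints.

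**The case against.** The strongest defence is that section 5 calls this a pilot and preliminary study, meant to inform larger ones. That limits the weight of the point but does not remove it: 25.1 plans hypothesis testing, and 5.3 ties the sample size to reaching significance. Labelling every analysis exploratory, with estimates and intervals, would also meet the concern, but the plan does not do that; it calls four endpoints primary and tests them.

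Three stronger readings are tempting and the documents do not support them.

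- **That a false claim for Boost is likely.** The 18.5% and 33.7% figures also count results showing Boost as worse. In Boost's favour only, the figures on these counts are 18.3% or less. They pass one half only if nearly independent tests are also run separately in each eye: 28 tests, 1 − 0.975^28 = 50.8%.
- **That two of the four primaries fall outside the hypothesis.** The sentence in 1.2 on expected evidence mentions only symptoms and wettability, but the hypothesis sentence before it also covers comfort and visual performance. Of the four primaries, only staining is absent from 1.2.
- **That the protocol declares success on any one endpoint.** It states no success rule. The calculation shows what happens if any one significant result is treated as success, which the text leaves open.

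It is also fair to object that the choice of primary endpoint belongs to the investigators. That stands, and the fix respects it.

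Finally, the named own-control comparison could let time or placebo change pass for a Boost effect. That is a separate bias, which a multiplicity adjustment would not cure.

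**Conclusion.** The point holds. The plan leaves the primary measure, visit, break-up reading and eye open, and tests them with no stated alpha, hierarchy or adjustment. The chance of at least one false positive is 18.5% for 4 and 33.7% for 8 independent tests, or 13–17% and 19–30% at correlations of 0.7 to 0.3. In Boost's favour only, it is 9.6% and 18.3%, or about 7–9% and 10–15% correlated, against 2.5% nominal.

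These sizes rest on the assumed 5% level, the assumed correlations and valid between-arm tests. Separate use of the break-up times, comfort instruments or eyes would raise them. The direction of the problem depends on none of these values, short of perfectly correlated tests. It should be corrected; it does not invalidate the design or require new data.

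**What to change.** In 9.1, before unblinding, state alpha and name one primary measure, one visit, one break-up reading and one rule for combining or choosing eyes, compared between the randomized arms. Then bring 10.2 and 25.1 into line.

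Two workable choices:

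- **CLDEQ-8 total at Visit 5.** Its questions look back over the past week, so at Visit 4, one day after treatment, the recall period lies mostly before treatment.
- **A single wettability reading at one named visit.** This is closer to the aim in 1.1 of showing that the coating is replenished.

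The choice is the investigators'. Test the other endpoints in a fixed order or with Holm, and label the remaining visits and readings exploratory. Alternatively, keep all four as primary at one named visit under Holm.

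The cost is wording only. With a single primary, the full alpha is kept, but endpoints not chosen can no longer carry a primary claim alone. If all four stay primary, the first Holm step needs about 1.29 SD rather than 1.06 SD at 80% power (15 per arm and 5% alpha assumed).
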